#### 9.2.16.5 Treatment Duration

Treatment duration (days) is defined as (Last Dose Date – First Dose Date + 1 day). Treatment duration indexed by the 28-day cycles is defined as ([Last Dose Date – First Dose Date + 1 day]/28 days), rounded to one decimal place.

## 9.2.17 Prior, Concomitant and Post treatment Medications

All medication verbatim terms reported on the electronic case report form (eCRFs) will be mapped according to the World Health Organization (WHO) Drug Dictionary (WHO DD March 2020 B3). The medications will be mapped to Anatomical/Therapeutic/Chemical (ATC) class and preferred names.

A prior medication is considered to be any medication that is taken within a year prior to the first study drug dosing.

A concomitant medication is considered to be any medication that is continued from Screening and continued after the first study drug dosing (i.e., a prior medication can also be a CM if it continued after the first dose of study drug) or any medication with start dates or stop dates within the Treatment Period. Specifically, CMs are medications: that are continued from Screening and continued after the first study drug dosing, or with start dates or stop dates within the first dose date through last dose date + 24 hours, missing CM end date, or ongoing) with the study drug administration.

Post medications is considered to be any medication taken after the last study drug dose date + 24 hours, missing CM end date, or ongoing.

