6.9.3 End-of-Treatment Visit

The EOT should be completed within \pm 7 days of the last dose of tarloxotinib. The following will be assessed or measured at EOT:

- Complete physical examination
- Weight
- Vital signs
- ECG (12-lead)
- Hematology panel
- Serum chemistry panel
- Pregnancy test
- Urine (dipstick acceptable)
- Blood sample for biomarkers (e.g., ctDNA)
- Concomitant medications
- Assess AEs
- Record the date and reason for the decision to discontinue study treatment

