6.10 Concomitant Medications and Treatments

All medications (prescription and over-the-counter) and blood products taken within 14 days of Cycle 1 Day 1 until the EOT will be recorded. The reason(s) for treatment, dose, and dates of treatment will be recorded. In addition, concomitant medications used to treat AEs occurring up to 30 days after the last dose of tarloxotinib will be recorded.

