## 9.2.18.1 Treatment-Emergent Adverse Events

Treatment-emergent adverse events are defined as any AEs, regardless of relationship to study drug, that have an onset or worsening in severity on or after the first dose of study drug until 30 days after the final dose of study drug (safety follow-up visit).

Related TEAEs are those reported by investigators as related to the study drug.

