#### 12.2 Prior and Concomitant Medications

Prior and concomitant medications (see definition in Section 9.2.10), will be summarized using WHO DD ATC class and preferred name. The summary results will be presented by cohort. Prior medications will be summarized by cohort. Concomitant medications will be summarized by cohort and overall.

These summaries will present the number and percentage of subjects using each medication. Subjects may have more than one medication within an ATC class and preferred name. At each summary level subjects are counted once if they reported one or more medications at that level. Each summary will be ordered by descending frequency of incidence of ATC class and preferred name within each ATC class.

All medications will be provided in a subject listing with flags indicating study drug dose level. The variables include, but not limited to: Start date/end date/ongoing, medication name, ATC class and preferred name, indication, dose, unit, form, frequency, and route.

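### SAP 9.2.17 closes the concomitant-medication window 24 hours after the last dose, out of line with Protocol 6.10 and the 30-day TEAE window, and its missing-or-ongoing clause leaves later drugs without a clear class

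*SAP*

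**What the plan says.** SAP 9.2.17 first describes a concomitant medication (CM) as one carried over from Screening past the first dose, or "any medication with start dates or stop dates within the Treatment Period". A second sentence then makes this specific: "with start dates or stop dates within the first dose date through last dose date + 24 hours, missing CM end date, or ongoing". That sentence has an unmatched closing bracket and runs on into a phrase about administration of study drug. The next paragraph reuses the same ending: "Post medications is considered to be any medication taken after the last study drug dose date + 24 hours, missing CM end date, or ongoing".

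Protocol 6.10 sets the collection rule. All medications "taken within 14 days of Cycle 1 Day 1 until the EOT will be recorded", and in addition "concomitant medications used to treat AEs occurring up to 30 days after the last dose of tarloxotinib will be recorded". Protocol 6.9.3 places the EOT visit within 7 days either side of the last dose. SAP 9.2.18.1 counts TEAEs "until 30 days after the final dose of study drug (safety follow-up visit".

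On reporting, SAP 12.2 tabulates prior medications by cohort and says "Concomitant medications will be summarized by cohort and overall". It plans no table of post medications, although all medications go into a subject listing. SAP 10.2.2.2 treats a CM with a missing stop date as ongoing. SAP Section 15, which sets out changes from the protocol, does not mention the 24-hour limit.

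**The concern.** Use of concomitant medications is a named safety endpoint in Protocol 4.2.2 and SAP 5.2, and SAP Section 4 gives a comprehensive safety analysis as a purpose of the plan. The protocol calls a drug given for an adverse event in the 30 days after the last dose concomitant. The SAP calls the same drug post once it starts more than 24 hours after that dose and has a stop date. SAP Section 4 says the SAP prevails where the two differ, so the narrower rule would be programmed. The event would then be counted in the TEAE tables while its treatment appeared in no medication table, and a reader of the report would not be told that the window had changed.

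The missing-or-ongoing clause adds a second difficulty. As worded it can admit a drug whatever its start date. Two subjects given the same drug on the same day for the same event could be classified differently only because one stop date is blank.

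**Working it through.** The plan gives no figure to reproduce, so the check applies the date rules directly. Days are counted from the last dose (day 0), and 24 hours is taken as one day.

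**Inputs**
- CM window closes: day +1 (SAP 9.2.17).
- TEAE window closes: day +30 (SAP 9.2.18.1).
- Protocol collection: all medications to EOT, which falls between day −7 and day +7; treatments for adverse events up to day +30 (Protocol 6.9.3 and 6.10).

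**Step 1: gap between the windows.** Days +2 to +30 count for TEAEs but not for CMs: 30 − 1 = 29 of 30 days (29/30 = 97%). For drugs taken for any reason, the gap up to EOT depends on the visit date. With EOT on day +7 it is days +2 to +7, that is 6 days. With EOT on or before day +1 it is 0.

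**Step 2: two readings of the clause.** Literal: an open end date (missing or ongoing) qualifies a drug by itself. Narrow: it qualifies only if the drug started by day +1.

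| Drug | CM, literal | CM, narrow | Post |
|---|---|---|---|
| Start +2, stop +6 | no | no | yes |
| Start +10, stop +20 | no | no | yes |
| Start +10, ongoing | yes | no | yes |
| Start +45, ongoing | yes | no | yes |
| Start −10, stop +20 | yes | yes | yes |

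**Step 3: all start days from +2 to +30.**
- Stop date recorded, on or before day +30: the start and stop combinations number 29 + 28 + … + 1 = 29 × 30 / 2 = 435. None is CM on either reading, and all 435 are post.
- End date open: 29 start days. On the literal reading all 29 are CM and all 29 are also post. On the narrow reading 0 of 29 are CM.

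**Step 4: what counts as open.** SAP 10.2.2.2 completes a stop date that has a year, or a year and month. Only a wholly missing stop date, or a drug marked ongoing, triggers the clause.

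**Step 5: the same cases under the fix proposed below.** A drug started on days +2 to +30 and recorded as treating an adverse event whose onset is no later than the drug's start has onset by day +30. All 435 dated combinations and all 29 open ones are then CM. A drug started on day +45 and ongoing, not given for such an event, is post only.

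**The case against.** The strongest reply is that little is lost. Late treatments with a stop date remain in the all-medications listing, with indication and dates. A drug started by day +1 and continued remains concomitant. Protocol 6.10 is a collection rule, and Protocol 9.7 sets no analysis window for medications. The trial stopped with 41 enrolled subjects and the SAP supports an abbreviated, descriptive report. All of this stands, and it limits the point to one summary table. It does not remove the unreported departure from the protocol's own use of the word concomitant.

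The reply also holds that the missing-or-ongoing clause, with the phrase about study drug administration that follows it, means ongoing during treatment. That reading is possible, and it keeps post-treatment starts out. It does not help with late adverse events: under it 0 of 29 open-ended late drugs are CM, so the mismatch with the TEAE window widens.

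Three stronger inferences are not supported:
- A reader might infer that late treatments disappear from the results. They leave the CM table, not the listing.
- A reader might infer that new anticancer drugs or other post-study drugs would be counted as concomitant. After EOT, Protocol 6.10 collects only treatments for adverse events, and the Schedule of Events shows no CM collection at the follow-up visit, so such drugs would probably not be in these data.
- A reader might turn the gap into a share of study time, for example 29/(50 + 30) = 36% for a last dose on Day 50, and take it as the share of medications lost. That is a share of calendar days; it counts neither drugs nor subjects.

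Overlap between CM and post is not in itself an error either. A drug taken during treatment and continued afterwards is properly both.

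**Conclusion.** The point holds in this limited form. The CM window covers 1 of the 30 post-dose days used for TEAEs, conflicts with Protocol 6.10, and is not declared in Section 15. Dated treatments started on days +2 to +30 for TEAEs are absent from every planned summary table on either reading of the rule. The class of open-ended ones depends on which reading is programmed: 29 of 29 start days are CM or none is.

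The effect is confined to a descriptive safety table. No efficacy result and no TEAE count changes. The documents do not give medication data, so the number of the 41 subjects affected is unknown and could be small. The conclusion assumes that the SAP text is programmed as written and that adverse-event treatments after EOT were recorded as Protocol 6.10 requires. The correction is worth making because the rule has two readings with opposite results and costs little to repair.

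**What to change.** Reword SAP 9.2.17 as follows in substance:
- Concomitant: any medication taken on or after the first dose that either started on or before the later of the EOT visit and last dose + 24 hours, or was recorded as treatment for an adverse event with onset up to 30 days after the last dose. Taking the later date matters, because an EOT visit up to 7 days before the last dose would otherwise close the window before that infusion.
- A missing or ongoing end date means only that the drug is still being taken. It never qualifies a drug by itself.
- Post only: all other drugs started after the window. Drugs started within it and continued afterwards may be both concomitant and post.

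Record the window in Section 15. Also correct the cross-reference in SAP 12.2, which points to Section 9.2.10 (Evaluable Subjects) for the medication definitions.

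The cost is a few sentences and one re-derived flag, with no new data. The flag relies on the recorded reason for treatment, which Protocol 6.10 requires and SAP 12.2 lists as the indication. CM counts may rise slightly.

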#### 9.2.18 Adverse Events

All AE verbatim terms reported on the eCRFs will be coded using the Medical Dictionary for Regulatory Activities (MedDRA® version 22.0). AE severity will be graded according to National Cancer Institute (NCI) Common Terminology Criteria for Adverse Events (CTCAE

2017) version 5. MedDRA will be used to map the AE verbatim to lowest level term, preferred term, and system organ class for summary purposes.

 Table 5
 Severity Grading Guideline for Adverse Events

Grade	Description
1	Mild; Asymptomatic or mild symptoms; Clinical or
	diagnostic observations only; Intervention not indicated
2	Moderate; Minimal, local or noninvasive intervention
	indicated; Limiting age-appropriate instrumental
	activities of daily living*
3	Severe or medically significant but not immediately
	life-threatening; Hospitalization or prolongation of
	hospitalization indicated; Disabling; Limiting self-care
	activities of daily living †
4	Life-threatening consequences; Urgent intervention
	indicated
5	Death related to adverse event

## 9.2.18.1 Treatment-Emergent Adverse Events

Treatment-emergent adverse events are defined as any AEs, regardless of relationship to study drug, that have an onset or worsening in severity on or after the first dose of study drug until 30 days after the final dose of study drug (safety follow-up visit).

Related TEAEs are those reported by investigators as related to the study drug.

## 9.2.18.2 Serious Adverse Events

Serious AEs are defined according to the NCI CTCAE v5.0, as described in Protocol Section 8.2.2 Adverse Event Severity.

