8.1.1.4 Serious Adverse Event (21 CFR 312.32(a))

An AE or suspected adverse reaction is considered "serious" if, in the view of either the Investigator or Sponsor, it results in any of the following outcomes:

- Death
- Life-threatening AE
- Inpatient hospitalization or prolongation of existing hospitalization
- Persistent or significant incapacity or substantial disruption of the ability to conduct normal life functions
- Congenital anomaly/birth defect.

Important medical events that may not result in death, be life-threatening, or require hospitalization may be considered serious when, based upon appropriate medical judgment, they may jeopardize the patient or may require medical or surgical intervention to prevent one of the outcomes listed in this definition. Examples of such medical events include allergic bronchospasm requiring intensive treatment in an emergency room or at home, blood dyscrasias or convulsions that do not result in inpatient hospitalization, or the development of drug dependency or drug abuse.

Amendment 3: 24 October 2020 Confidential and Proprietary

Rain Therapeutics Inc.

8.1.1.5 **Serious Unexpected Suspected Adverse Reaction**

A suspected adverse reaction that is both serious and unexpected will be reported in an expedited manner.

Rain Therapeutics (or designee) will report all serious unexpected suspected adverse reactions (serious, related, and unexpected AEs) to the regulatory agencies in the countries where this study is conducted per local country requirements.

- Regulatory agencies will be notified (e.g., by telephone, facsimile transmission, or in writing) of all fatal and/or life-threatening suspected adverse drug reactions as soon as possible but no later than 7 calendar days after first knowledge by the Sponsor that a case qualifies, followed by as complete a report as possible within 8 additional calendar days.
- Serious, unexpected suspected adverse reactions that are not fatal or life-threatening must be filed as soon as possible but no later than 15 calendar days after first knowledge by the Sponsor that the case meets the minimum criteria for expedited reporting.

8.2 **Adverse Events Reporting**

8.2.1 **Adverse Event Term**

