AEs must be reported using standard medical terminology. The use of abbreviations (standard and nonstandard) should be avoided to help ensure a clear understanding of the event. An example of a standard abbreviation that may have several meanings is "MI" which could mean "myocardial infarction" or "mitral insufficiency." All AE terms will be coded using a standardized dictionary (i.e., Medical Dictionary for Regulatory Activities [MedDRA®]). Generally, when reporting a well-known and understood condition, it is preferable to report the overall diagnosis rather that the individual signs and symptoms; the exception to this rule in this study is when the patient experiences an infusion reaction (i.e., infusion-related reaction). The term "intermittent" should be avoided as the duration and incidence of events helps in understanding the safety profile of the study drug.

8.2.2 **Adverse Event Severity**

AEs will be reported at the highest experienced. AE severity will be graded according to NCI CTCAE v5.0. A copy of the document will be provided to investigational sites and an electronic version is available at:

https://ctep.cancer.gov/protocolDevelopment/electronic applications/docs/CTCAE v5 Quick R eference 8.5x11.pdf

Events not listed in NCI CTCAE will be graded according to the criteria described in Table 10.

Confidential and Proprietary

Table 10: Severity Grading Guideline for Adverse Events Not Listed in NCI CTCAE

Adverse Events Not Listed in NCI CTCAE v5.0			
Grade	Description		
1	Mild; Asymptomatic or mild symptoms; Clinical or diagnostic observations only; Intervention not indicated		
2	Moderate; Minimal, local or noninvasive intervention indicated; Limiting age-appropriate instrumental activities of daily living*		
3	Severe or medically significant but not immediately life-threatening; Hospitalization or prolongation of hospitalization indicated; Disabling; Limiting self-care activities of daily living**		
4	Life-threatening consequences; Urgent intervention indicated		
5	Death related to adverse event		

Adapted from NCI CTCAE v5.0

NCI CTCAE = National Cancer Institute Common Terminology Criteria for Adverse Events

Note: A semicolon indicates "or" within the description of the grade.

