#### 4 PURPOSE OF THE ANALYSIS PLAN

This statistical analysis plan (SAP) pre-specifies the statistical analysis methods for supporting the completion of the abbreviated clinical study report (CSR) of Study RAIN-701 for investigational product tarloxotinib, a novel drug candidate designed to treat subjects with advanced solid tumors with qualifying genetic mutations and/or fusions. The study intended to enroll up to 215 subjects across 5 cohorts but was discontinued early on the basis of a business decision made by the sponsor. At the time of the database lock for RAIN-701 (23 April 2021), 41 subjects were enrolled. This SAP will be used to conduct a comprehensive safety analysis and summarize the available efficacy data collected during the study. The primary, secondary, and efficacy analyses planned in the protocol may not be appropriate or possible based on the available data. The planned analyses identified in this SAP may be included in future manuscripts.

The analysis methods described in this plan are considered *a posterior*, in that they have been defined after the clinical database lock. Exploratory analyses that are not defined in this SAP may be performed to support the clinical development program. Any post-hoc or unplanned analyses that are performed for the CSR, but not defined in this SAP, will be documented in the CSR. Changes from the planned analyses stated in the study protocol are described in Section 15. Should the SAP and the protocol be inconsistent with respect to any further planned analyses, the language of the SAP is governing.

Version 1.0, 14 October 2022

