#### 9.2.18.3 Severe Adverse Events

Severe AEs are defined as events with a severity of Grade 3 or higher.

\* Instrumental activities of daily living refer to preparing meals, shopping for groceries or clothes, using the telephone, managing money, etc.

† Self-care activities of daily living refer to bathing, dressing and undressing, feeding self, using the toilet, taking medications, and not bedridden

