## 9.2.18.4 Serious Unexpected Suspected Adverse Reaction

A serious AE deemed related to the study drug (adverse reaction) is considered "unexpected" if it is not listed in the Investigator's Brochure (i.e., ECG QT prolonged, Hypertension, Rash [rash, infusion site rash and rash erythematous]) or is not listed at the specificity or severity that has been observed.

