#### 14.1 Adverse Events

Safety will be assessed by repeated clinical evaluations including adverse events (AEs), serious AEs (SAEs), serious unexpected suspected adverse reactions (SUSARs), and deaths.

Safety data will be summarized descriptively. AEs will be summarized by severity, seriousness, and relationship to study drug. All AEs including the AE verbatim term and the associated AE MedDRA preferred term will be provided in the subject data listings. Incidence of treatment-emergent AEs will be summarized descriptively by cohort and total.

TEAEs are defined in Section 9.2.18.1. All reported AEs (including non-TEAEs) will be listed. Separate listings will be provided for suspected adverse reactions, unexpected events, SAEs, and serious unexpected suspected adverse reactions. All TEAE summary tables will present the number and percentages of subjects reporting TEAEs, unless otherwise specified. A summaries of TEAEs by severity, seriousness, and relation to study drug will be tabulated.

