## 14.1.1 Overall Summary of TEAEs

Overall summary of TEAEs will be presented by cohort and overall. Subjects will be counted only once at the highest severity when summarizing TEAE by severity. The overall summary will include the following:

- Number (%) of subjects with any TEAEs
- Number (%) of subjects with any TEAEs by severity
- Number (%) of subjects with any serious TEAEs
- Number (%) of subjects with any related TEAEs
- Number (%) of subjects with any serious unexpected suspected adverse reactions

- Number (%) of subjects with any TEAEs leading to study drug discontinuation
- Number (%) of subjects with any AEs leading to death

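### SAP 9.2.18.2 defines serious adverse events by a reference to severity grading, so the serious-TEAE and SUSAR outputs have no usable definition

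*SAP*

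**What the plan says.** SAP 9.2.18.2 gives the whole definition in one sentence: "Serious AEs are defined according to the NCI CTCAE v5.0, as described in Protocol Section 8.2.2 Adverse Event Severity". The next subsection, 9.2.18.3, reads "Severe AEs are defined as events with a severity of Grade 3 or higher". The SUSAR definition in 9.2.18.4 opens "A serious AE deemed related to the study drug (adverse reaction) is considered" and goes on to what makes such an event unexpected, so it takes its notion of serious from 9.2.18.2.

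The cited Protocol 8.2.2 states "AE severity will be graded according to NCI CTCAE v5.0" and supplies a Grade 1 to 5 table for events that CTCAE does not list. Protocol 8.1.1.4 defines serious elsewhere and differently: an event is serious if "in the view of either the Investigator or Sponsor, it results in any of the following outcomes", followed by death, a life-threatening event, inpatient or prolonged hospitalization, incapacity and birth defect. It also allows for important medical events.

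SAP 14.1 plans that "AEs will be summarized by severity, seriousness, and relationship to study drug". SAP 14.1.1 includes the row "Number (%) of subjects with any serious TEAEs" and a SUSAR row. SAP 14.1.2 and 14.1.3 repeat both as tables, and 14.1 adds SAE and SUSAR listings. On precedence, SAP Section 4 says: "Should the SAP and the protocol be inconsistent with respect to any further planned analyses, the language of the SAP is governing".

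**The concern.** Severity and seriousness are different properties of an event. Severity is intensity on a graded scale; seriousness is a matter of outcome or medical importance. The SAP sends the reader to the severity scale for the definition of serious. A programmer who follows it finds five grades and no statement of which of them is serious.

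This matters because SAP Section 4 makes a comprehensive safety analysis a main use of the plan, while efficacy is reduced to descriptive summary. Serious-event and SUSAR counts are central results of such a report. SAP Section 15 lists departures from the protocol, down to dictionary versions, but not this one, so a reader of the report would assume that the protocol's definition had been used.

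**Working it through.** The documents state no figure to reproduce. The check compares the texts, traces the outputs, and then gives one illustrative calculation.

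**1. What the cited section contains.** Protocol 8.2.2 holds CTCAE v5.0 grading and the fallback table. It has no seriousness criterion and no grade at which an event becomes serious. Every AE receives a grade, so the reference on its own selects either all AEs or none.

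**2. What the protocol means by serious.** Protocol 8.1.1.4 is outcome-based. Protocol 8.5 applies the distinction to this drug's main toxicity: Grade 3 or Grade 4 QTc prolongation is reported as an AESI, and as an SAE only if 8.1.1.4 is also met. Grade 3 alone therefore does not make an event serious.

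**3. Possible readings of SAP 9.2.18.2.**

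| Reading | Set of events | Consequence |
|---|---|---|
| Literal | None identifiable | Outputs undefined |
| Grade 3 or higher | Same as severe in 9.2.18.3 | Serious tables duplicate severe tables; events misclassified |
| Mistaken cross-reference for 8.1.1.4 | Protocol SAEs | Counts right, text wrong |

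Nothing in the SAP says which reading applies, and no sentence names the investigator-reported SAE classification as the data source.

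**4. Outputs affected.** These are the SUSAR definition (9.2.18.4), the SAE and SUSAR listings (14.1), the serious-TEAE and SUSAR rows (14.1.1), and the corresponding tables by system organ class and preferred term (14.1.2) and by preferred term (14.1.3). Under a Grade 3 or higher reading, SAP 10.2.2.1 adds another route to error: an AE with unrecorded severity is imputed as severe and would then also become serious.

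**5. Illustration of size under a Grade 3 or higher reading.** Inputs: 19 of 51 patients with Grade 3 QT prolongation across the two earlier Phase 2 studies (Protocol 2.3.2), and 41 subjects enrolled (SAP Section 4).

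- Rate: 19/51 = 37.3%, exact (Clopper-Pearson) 95% CI 24.1% to 51.9%.
- Applied to RAIN-701: 41 × 0.373 = 15.3, or about 15 subjects. The limits give 41 × 0.241 = 9.9 and 41 × 0.519 = 21.3, or about 10 to 21.

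Those subjects would count as having a serious TEAE on Grade 3 QTc prolongation alone, except that any who also met 8.1.1.4 would be counted correctly. In the other direction, a Grade 2 event leading to inpatient hospitalization would be omitted; the documents give no figure for such events.

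The calculation assumes that the earlier rate carries over. The earlier studies had different populations and central ECG reading, whereas RAIN-701 ECGs are read locally (Protocol 8.5). Protocol 2.3.2 also calls the earlier data preliminary.

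**The case against.** A reader might infer that every serious-TEAE and SUSAR table will count the wrong events, or that most subjects will be tabulated as having a serious event because 17 of 21 (81%) in the earlier NSCLC study had Grade 3 AEs. The documents do not support either inference, for these reasons:

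- SAP 9.2.18.2 has no cut-off, so it does not impose Grade 3 or higher.
- The SAP defines severe separately, lists severity and seriousness as separate summaries, and requires both a severe and a serious table in 14.1.2 and 14.1.3. Under a Grade 3 or higher reading these would be identical, which makes that reading unlikely.
- The sentence claims to follow the protocol, and Section 15 declares no change. A wrong cross-reference is at least as plausible as an intended new definition.
- The two concepts overlap. SAP Table 5 puts indicated hospitalization and disability at Grade 3, life-threatening events at Grade 4 and death at Grade 5.
- Investigators were required to report SAEs during the trial (Protocol 8.3), and the database was locked on 23 April 2021, before the SAP of 14 October 2022. The SAP sentence cannot have altered what was reported.
- The QT figure says little about SUSARs. SAP 9.2.18.4 names QT prolongation as listed in the Investigator's Brochure, so it is expected unless its severity or specificity was unlisted.

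All of this stands, and it limits the consequence. It does not repair the definition. Database lock protects the collected data but not the derivation that this SAP controls. The precedence clause in Section 4 concerns further planned analyses; whether it reaches the SAE classification is arguable, but it stops a reader from simply falling back on the protocol.

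**Conclusion.** The definition is wrong as written. It points to severity grading where Protocol 8.1.1.4 uses outcome, the departure is undeclared, and the serious-TEAE and SUSAR outputs rest on it. The supportable conclusion is that those outputs are undefined, and would be misclassified if the sentence were programmed as a grade rule. Actual miscounting is not established: if the tables use the SAE classification made during the trial under 8.1.1.4, the counts will be right despite the text.

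The number affected in RAIN-701 cannot be derived. The estimate of about 15 of 41 subjects (10 to 21) holds only if serious is read as Grade 3 or higher and the earlier Phase 2 QT rate applies. No figure supports a size for the SUSAR outputs. Correction is still warranted, because safety is the main content of the report and the change is small.

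**What to change.** Replace SAP 9.2.18.2 with: *Serious AEs are events meeting the criteria of Protocol Section 8.1.1.4, as classified by the investigator or sponsor.* Name the dataset and variable that hold this classification. Do not assume a seriousness flag on the AE form: neither document describes one, and Protocol 8.3 describes SAEs as submitted on a separate report. State that 9.2.18.4 starts from the corrected definition, and keep Grade 3 or higher for severe AEs in 9.2.18.3 only.

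If the outputs have already been produced, check which rule the programs used and re-run the serious-TEAE and SUSAR tables and listings only if it was a grade rule.

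The cost is one replaced sentence and one named data source. No new data collection should be needed, since SAEs had to be reported during the trial, but the sponsor must confirm where the classification is held.
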